#### **6.7.8.7. Attack Duration**

The duration of each subject-reported attack will be calculated in hours, based on the start and stop date and time of the subject-reported attack (time the attack finished). For an adjusted attack that includes more than one subject-reported attack, the duration is calculated from the start of the first subject-reported attack to the end of the last subject-reported attack that has been combined into one adjusted attack. Similarly, the duration of the attack from start of the attack to time that the worst was over will also be calculated.

All subject-reported attack durations will be included in listings and those included in adjusted attacks will be denoted. Adjusted attack duration will be summarized.

#### **6.7.8.8. Attack Onset Relative to Initial Dose of Study Drug**

The time to onset of each subject-reported attack from the time of the initial dose of study drug reported in the subject eCRF page will be calculated and displayed in the listing of attack information. If there is no dosing time reported for the dose taken prior to the attack, the attack onset time relative to prior dose will be missing. The attack onset time relative to prior dose of study drug is information used in the listing of attack data only.

#### **6.7.8.9. Medications to Treat HAE Attacks**

The following medications reported taken as acute treatment in the subject diary will be classified in the analyses as targeted medications to treat subject-reported HAE attacks: Berinert, Cinryze, Kalbitor, Firazyr, Ruconest, and fresh frozen plasma.

The following medications, also recorded in the subject diary as HAE treatments, will be classified as non-targeted medications: pain medication, nausea medication, intravenous fluids, other.

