8.2. Subject Selection

8.2.1. Inclusion Criteria

Subjects must meet all of the following inclusion criteria to be eligible for participation in this study:

1. Males and nonpregnant, nonlactating females ≥ 18 years of age (main study) or ≥ 12 to 17 years of age (substudy).
2. Subjects with a clinical diagnosis of HAE Type I or II who, in the opinion of the Investigator, are expected to benefit from an oral treatment for the prevention of angioedema attacks. A clinical diagnosis of HAE Type I or II is defined as:
 - A C1 esterase inhibitor (C1-INH) functional level below the assay lower limit of normal as assessed during the screening period by chromogenic assay OR
 - Laboratory documentation of historical C1-INH functional level below the assay lower limit of normal OR
 - Subjects who currently use plasma derived or recombinant C1-INH based therapies for acute attacks or prophylaxis may use one of the following to confirm their diagnosis:
 - SERPING-1 gene mutation known or likely to be associated with HAE Type I or II as assessed during the screening period OR
 - A confirmed family history of C1-INH deficiency
3. Subject weight ≥ 40 kg.
4. Access to one or more targeted medications for the treatment of acute HAE attacks. The following are acceptable: icatibant, plasma-derived C1-INH (any form), ecallantide, recombinant C1-INH.
5. Female subjects must meet at least 1 of the following requirements:

- a. Be a woman of childbearing potential (defined as a nonmenopausal adult or adolescent-female who has not had a hysterectomy, bilateral oophorectomy, or documented ovarian failure) who agrees to use at least an acceptable effective contraceptive method during the study and for a duration of 30 days after last dose of study drug. One or more of the following methods are acceptable:
- Surgical sterilization (ie, bilateral tubal occlusion or vasectomy of male partner)
 - Placement of an intrauterine device (IUD) or intrauterine system (IUS) (implanted any time prior to or during screening)
 - Implantable or injectable progesterone hormonal contraception initiated at least 7 days prior to the screening visit
 - Combined (estrogen- and progestogen-containing) oral, intravaginal, or transdermal or oral progesterone norethindrone-based hormonal contraception initiated at least 28 days prior to the screening visit
 - Male or female condom with or without spermicide

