**Diagnosis and main criteria for inclusion (see protocol section 8.2):**

*Inclusion Criteria:*

- 1) Males and non-pregnant, non-lactating females  $\geq 18$  years of age (main study) or  $\geq 12$  to 17 years of age (substudy)
- 2) Subjects with Type I or Type II HAE who either have:
  - a) Participated in a BCX7353 study OR
  - b) In countries open to recruitment of treatment-naïve subjects under a prior version of Protocol BCX7353-204:

In the opinion of the Investigator, subjects are expected to benefit from an oral treatment for the prevention of angioedema attacks and have a clinical diagnosis of HAE Type I or II, defined as having a C1 esterase inhibitor (C1-INH) functional level below 50% and a complement 4 (C4) level below the lower limit of the normal (LLN) reference range, as assessed during the screening period.

In the absence of a low C4 value drawn during the intercritical period (ie, subject is not having an HAE attack), 1 of the following is acceptable to confirm the diagnosis of HAE: 1) a SERPING-1 gene mutation known or likely to be associated with HAE Type I or II assessed during the screening period; 2) a confirmed family history of C1-INH deficiency; 3) a C4 redrawn and retested during an attack with the results below the LLN reference range measured during the screening period

For subjects with a C1-INH function  $\geq 50\%$  but less than the assay LLN, a SERPING-1 gene mutation known or likely to be associated with HAE Type I or II, assessed during the screening period OR a repeat C1-INH functional test  $< 50\%$  will be considered acceptable for enrollment.
- 3) Subject weight  $\geq 40$  kg
- 4) Access to appropriate medication for the treatment of acute HAE attacks
- 5) Agreement to use acceptable effective contraception
- 6) Able to provide written, informed consent. Subjects aged  $\geq 12$  to 17 years who are screening for the substudy must be able to read, understand, and be willing to sign an assent form in addition to a caregiver providing informed consent
- 7) In the opinion of the Investigator, the subject is able to adequately comply with all required study procedures for the duration of the study. The subject must demonstrate adequate compliance with all study procedures required including diary recording of HAE attacks

*Exclusion Criteria:*

- 1) Pregnancy or breast feeding or planned pregnancy during the study period.

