**Table 2: Protocol Revision Chronology**

Protocol	Date	Key Information
Protocol Version 1.0	20 September 2017	Original
Protocol Version 2.0	5 December 2017	Made administrative clarifications, changed design to include 2 dose groups, increased sample size, removed option to reduce dose, AECT assessment removed, updated prohibited medications
Protocol Version 3.0	6 December 2017	Made administrative clarifications, expanded inclusion criteria to include subjects naïve to BCX7353 in selected countries
Protocol Version 4.0	5 October 2018	Made administrative clarifications, expanded subject numbers, expanded inclusion criteria, extended study duration to 96 weeks, added study data, and clarified discontinuation criteria
Protocol Version 5.0	7 February 2019	Expanded subject numbers, added US sites, added subjects with recent androgen use.

Abbreviations: AECT = Angioedema Control Test; US = United States.

This SAP was developed in accordance with International Council for Harmonisation (ICH) E9 guideline. The purpose of this document is to provide details on the statistical methodology used to analyze the safety and effectiveness for Study BCX7353-204. Study population definitions, derivations of variables, handling of missing data, and other information necessary for analysis of study data are provided. Planned tables, figures, and listings are specified. All decisions regarding final analysis, as defined in this SAP document, will be made prior to database lock of the study data. Further information can be found in the protocol and electronic Case Report Forms (eCRFs).

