## 7.6. HAE Medical and Medication History

HAE and HAE medication history will be summarized for the following where possible:

- HAE history
- Past on-demand treatments of HAE
- Current on-demand treatments of HAE
- Past prophylactic treatments of HAE

Past on-demand treatments will include those medications that were taken as needed and discontinued prior to the initiation of study treatment as recorded on the HAE Medication History Page. Past prophylactic treatments will include those medications that were taken as prophylaxis and discontinued prior to the initiation of study treatment as recorded on the HAE Medication History Page. Current on-demand medications will include those that are noted at screening as currently used for on-demand treatment as recorded on the HAE Medication History Page. Summaries will include a grouping of any C1-INH medication as well as displays of individual medications. The C1-INH grouping will include plasma-derived C1-INH replacement (brand names = Cinryze, Berinert, Haegarda), recombinant C1-INH replacement (brand name = Ruconest), icatibant (brand name = Firazyr), Ecallentide (brand name = Kalbitor), fresh frozen plasma, and lanadelumab (brand name = Takhzyro). The summary of androgens will

include androgens (unspecified), oxandrolone, danazol (brand name = Danocrine), and stanozolol.

For subjects who are not rolling over from a previous BCX7353 study, a summary of screening complement 4 (C4) and functional C1 esterase inhibitor (C1-INHf) will be provided in categories showing how subjects met the inclusion criteria confirming diagnosis of Type I or II HAE. Confirmation by SERPING, if required, will be included in the summary. Categories for C4 will be  $C4 < \text{lower limit of normal (LLN)}$  and  $C4 \geq \text{LLN}$  and for C1-INHf will be  $< 50\%$ ,  $50\%$  to  $< 74\%$ , and  $\geq 74\%$ . Where the C4 test has been repeated, the test result for the repeat will be used in this summary.

In addition, detailed SERPING data will be listed.

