#### **8.3.1.6. Use of HAE Attack Medications**

Use of HAE medications as noted in the diary will be summarized separately from concomitant medications as noted in Section 7.7. In addition, summaries of the number of subject-reported HAE attacks requiring treatment will be provided.

The time to first use of HAE targeted rescue medication for an adjusted attack will be estimated using Kaplan-Meier estimates. Subjects who do not use HAE rescue medication will be censored at the time of study treatment discontinuation.

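### The SAP classes targeted acute medication by a closed brand list plus fresh frozen plasma, while the protocol goes by substance, so some first-rescue times can be misclassified in either direction

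*SAP*

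**What the plan says.** SAP 6.7.8.9 sorts the acute treatments recorded in the diary into two groups. The targeted group is "Berinert, Cinryze, Kalbitor, Firazyr, Ruconest, and fresh frozen plasma". The remaining entries "will be classified as non-targeted medications: pain medication, nausea medication, intravenous fluids, other". The section has no rule for recoding an *other* entry that turns out to be a targeted substance.

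Protocol 8.2.1, inclusion criterion 4, requires access to at least one targeted medication for acute attacks and lists them by substance: "The following are acceptable: icatibant, plasma-derived C1-INH (any form), ecallantide, recombinant C1-INH". Fresh frozen plasma is not there, nor in the parallel list in protocol 5.4.4.

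SAP 7.6 links substances to brands: "plasma-derived C1-INH replacement (brand names = Cinryze, Berinert, Haegarda" for the plasma-derived class, and "recombinant C1-INH replacement (brand name = Ruconest), icatibant (brand name = Firazyr), Ecallentide (brand name = Kalbitor" for the other three.

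The classification feeds SAP 8.3.1.6: "The time to first use of HAE targeted rescue medication for an adjusted attack will be estimated using Kaplan-Meier estimates". Subjects without such use are censored when study treatment stops. The displays are Table 14.2.1.18 and Figure 14.2.1.19. SAP section 11, on changes from the protocol's analyses, does not mention the difference between the lists.

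**The concern.** Both documents use the word targeted, but one defines it by substance and the other by brand. A brand list with a non-targeted residual category misclassifies any accepted product recorded under another name: Haegarda, another plasma-derived C1-INH, or icatibant not entered as Firazyr. If a subject uses such a product first and a listed one later, the event comes late. If the subject uses only such products, there is never an event, and the subject stays in the curve as rescue-free until treatment stops.

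Fresh frozen plasma has the opposite effect: use of it counts as an event under the SAP but would not under the protocol's list.

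At stake is the reading of one Kaplan-Meier table and figure, and of any split of treated attacks into targeted and non-targeted.

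**Working it through.** **Side by side**

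| Protocol class | Brands in SAP 7.6 | On the 6.7.8.9 list |
|---|---|---|
| Icatibant | Firazyr | Firazyr |
| Plasma-derived C1-INH, any form | Cinryze, Berinert, Haegarda | Cinryze, Berinert |
| Ecallantide | Kalbitor | Kalbitor |
| Recombinant C1-INH | Ruconest | Ruconest |
| Not listed | Fresh frozen plasma | Fresh frozen plasma |

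Every class has at least one brand on the list. The gaps are within class, plus the added plasma. The plan states no time-to-rescue figure, so there is nothing to reproduce; what follows only sizes the effect.

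**Inputs** (protocol 5.2.2, interim data)
- Adjusted attacks treated with any medication: 85.4%; with SOC-Rx: 81.6%.
- Month 1 attack rate, in the 73 subjects on 150 mg treated through Week 48: mean m = 1.18, SD 1.40 per 28 days.

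**Assumptions:** SOC-Rx, which the documents do not define, equals the SAP list; every attack is equally likely to be treated; subject rates are constant over time.

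**Ceiling on omitted products.** 85.4 − 81.6 = 3.8 points of attacks, and 3.8 / 85.4 = 4.4% of treated attacks. This gap also contains genuinely non-targeted treatment, so it is an upper limit.

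**Effect on the median.** With p the share of attacks counted as targeted:
- exponential: 28 × ln 2 / (m × p)
- gamma-Poisson: 28 × k × (2^(1/k) − 1) / (m × p), with k = 1.18² / (1.40² − 1.18) = 1.3924 / 0.78 = 1.79

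| | Exponential | Gamma-Poisson |
|---|---|---|
| p = 0.816 (SAP list) | 20.2 days | 24.6 days |
| p = 0.854 (every treated attack is targeted) | 19.3 days | 23.5 days |

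The difference is about 1 day. If the gap instead sits entirely in a share q = 4.4% of subjects who use only off-list products, the observed curve is q + (1 − q) × S(t), with S(t) taken at p = 0.854. The medians are then 20.6 against 19.3 days, or 25.5 against 23.5 days: at most about 2 days.

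**Effect on the tail.** The same q moves late estimates more in relative terms. With the Month 6 rate in the same subjects (mean 1.01, SD 1.26), k = 1.0201 / 0.5776 = 1.77. At p = 0.854 and t in 28-day months, S(t) = (1 + 1.01 × 0.854 × t / k)^(−k).
- Week 24 (t = 6): 8.9% becomes 0.044 + 0.956 × 0.089 = 13.0%.
- Week 48 (t = 12): 3.3% becomes 7.6%.

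These are ceilings, not estimates.

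**Net direction.** Let o be the share of attacks treated only with omitted products and f the share treated only with fresh frozen plasma. The protocol-based share is 0.816 − f + o. Shift in the gamma-Poisson median, SAP list minus protocol classes:

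| o | f | Shift (days) |
|---|---|---|
| 3.8% | 0 | +1.1 |
| 2% | 2% | 0 |
| 1% | 2% | −0.3 |
| 0 | 2% | −0.6 |
| 0 | 4% | −1.3 |

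The documents give neither o nor f, so these values are assumed, and the sign changes within a plausible range.

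**The case against.** A reader might infer that time to first rescue is biased long, in favour of the drug. That follows only if fresh frozen plasma is ignored. With both departures in play the net sign is open.

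A reader might also suppose that 10% or 20% of subjects use only off-list products. Nothing in the documents supports such shares. The interim gap is far smaller (subject to the SOC-Rx assumption), and Berinert and Firazyr, reported as the most used products, are both listed.

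A third inference is that the SAP predates US recruitment. Its revision table ends at Version 5.0, described as "Expanded subject numbers, added US sites, added subjects with recent androgen use", so US sites were already in view. What does hold is that the SAP plans for about 225 subjects and the protocol for about 475, about 250 of them in the US, while the interim cohort was mainly non-US. Its product mix may not carry over.

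Other objections have more force. Haegarda is the only omitted brand the documents name, and they otherwise show it as prophylaxis (protocol Table 2, SAP 6.7.5). The same sections treat Cinryze as prophylaxis, though, and 6.7.8.9 still counts it when taken acutely. The diary's answer options are not shown, so sites may well enter other icatibant under Firazyr. Criterion 4 governs access rather than analysis, and the SAP's own version says only "Access to appropriate medication for the treatment of acute HAE attacks", so part of the mismatch may come from protocol versions. Fresh frozen plasma sits with HAE-specific agents in SAP 7.6, so counting it is consistent within the SAP, and dropping it as an event is a choice rather than a correction.

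The reach is also limited. Adjusted-attack status in SAP 6.7.8.2 depends on treated versus untreated, so attack rates do not change. Time to targeted rescue is absent from the endpoints in SAP 3.2.2, and SAP 8.1 rules out formal testing.

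**Conclusion.** The inconsistency is real and appears in the text. The SAP states a rule that, applied literally, treats accepted targeted products as non-targeted when they are recorded under an off-list name, and it conflicts with the SAP's own drug classes in 7.6. Omitted products push time to first targeted rescue longer and fresh frozen plasma pushes it shorter; the documents do not settle the balance.

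The omission effect is small on interim evidence: no more than about 4.4% of treated attacks and about 1 to 2 days on the median. That rests on SOC-Rx being the SAP list, on the simple rate models used, and on interim subjects representing later ones. How off-list products reach the database is unknown. Severity is minor, but the wording should be settled before lock.

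**What to change.** In SAP 6.7.8.9, define targeted medication by active substance in line with protocol inclusion criterion 4: any icatibant, any plasma-derived C1-INH including Haegarda, ecallantide, and any recombinant C1-INH, with brands as examples only. State that *other* diary entries coding to these substances in WHODD, the dictionary already used in SAP 7.7, are reclassified as targeted before database lock. Show fresh frozen plasma on its own row, state how it is classed and why, and add a sensitivity summary of time to first targeted rescue that does not count it as an event. Record the definition in SAP section 11 if it still differs from the protocol.

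The cost is a paragraph of SAP text, a small coding map for *other* entries, and one extra summary. The rescue-free curve may look slightly less favourable once the omitted products are counted.

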#### **6.7.8.10. Time to First Use of HAE Rescue Targeted Medication for an Adjusted Attack**

For each subject, the time to first use of HAE targeted rescue medication to treat an adjusted attack will be calculated as the number of days from the first dose of study drug to the first use of rescue medication.

### 6.7.8.11. Attack Symptoms

Symptoms reported for adjusted attacks will be included in summaries of attack characteristics. In addition, listings of diary data will show symptoms for all subject reported attacks.

### 6.7.8.12. Attack Location

The anatomical location of each subject-reported and adjusted attack will be determined based on the symptoms indicated in the diary as shown in [Table 6](#).

**Table 6: Determination of Attack Location Using Symptoms Collected in the Diary**

Abdominal-Only Attack	Mixed Attack	Peripheral Attack (Inclusive of Skin and Airway Swelling)
Symptoms checked must only come from this box: Internal swelling or symptoms of internal swelling in the abdomen: Nausea Abdominal discomfort Cramps (colicky pain) Vomiting Abdominal pain Diarrhea	Must have at least 1 symptom from left and right box (from abdominal and peripheral attack characterization)	Symptoms checked must only come from this box: Visible swelling: face/head neck (outer swelling) legs, buttocks/genitals eyes arms feet stomach (outside) mouth/tongue/lips hands chest/back joints Internal swelling or symptoms of internal swelling of the airways: lump in throat/tightness change in voice difficulty swallowing difficulty breathing Pink rings (erythema marginatum)

Note: Symptoms of headache and substantial fatigue may be checked by the subject but play no role in the characterization of the location of a subject-reported attack.

### 6.7.8.13. Attack Triggers

Attack triggers for adjusted attacks will be summarized with the attack characteristics for adjusted attacks. In addition, attack triggers for each subject-reported attack will be included in the listings.

#### 6.7.8.14. AE-QoL

The AE-QoL (Weller, Groffik et al. 2012) consists of 4 domains and a total score. Each item answered by the subject scores between 0 and 4 points depending on the answer option chosen by the subject. The first answer option gets 0 points, the second option 1 point, the third option 2 points, etc. Dimensions of the AE-QoL are shown in Table 7.

**Table 7: Dimensions of the AE-QoL**

Dimensions	Item
Functioning	1. Impairment of work
	2. Impairment of physical activity
	3. Impairment of spare time activities
Fatigue/Mood	4. Impairment of social relations
	6. Difficulties of falling asleep
	7. Waking up during the night
	8. Feeling tired during the day
	9. Difficulties in concentrating
	10. Feeling downhearted
Fears/Shame	12. Feeling burdened at having swellings
	13. Fear of new suddenly appearing swellings
	14. Fear of increased frequency of swellings
	15. Ashamed to visit public places
	16. Embarrassed by the appearance of swellings
	17. Fear of long-term negative drug effects
Nutrition	5. General limitations in foods and eating
	11. Limitations in the selection of food and beverages
Total Score	Items 1 to 17

Abbreviations: AE-QoL = angioedema quality of life questionnaire.

The AE-QoL domain scores and the AE-QoL total score are calculated using the following formula:

$$\text{AE-QoL Domain Score} = \frac{\sum \text{items}}{\max(\sum \text{items})} * 100$$

where

$\sum \text{items}$  = Sum of reported item scores per case report form

$\max(\sum \text{items})$  = Sum of the Maximum possible score for each domain

The calculated AE-QoL domain scores range from 0 (best) to 100 (worst).

The calculated AE-QoL ranges from 0 (best) to 100 (worst).

Since only answered items are included in the computation (and the calculated domain and total scores are not raw scores but linear transformations to a 0 to 100 scale), the calculated scores are not or only little influenced by missing items. An AE-QoL domain scores will not be calculated if more than one item is left unanswered in that domain. The AE-QoL total score will not be calculated if more than 25% of items (ie, > 4 items) are left unanswered. Note that subjects who do not work were instructed to leave question 1 blank. As long as that is the only question in the functioning domain that is missing, the functioning domain can still be calculated.

